# 3.6 Stopping Rules and Discontinuation Criteria

There are no formal rules for early termination of this study. During the conduct of the study, SAEs will be reviewed (see Section 8.1.4) as they are reported from the study centre to identify safety concerns. An Expert Committee will be appointed to review safety data. This Expert

**PAGE 33/103** 

Committee will be chaired by the principal investigator. Full details of the operating model for this safety data review will be provided in a charter to be produced.

The study may be terminated by the sponsor at any time.

A subject may discontinue participation in the study at any time for any reason (e.g. lack of efficacy, withdrawal of consent, AE). The investigator and/or sponsor can withdraw a subject from the study at any time for any reason (e.g. protocol violation or deviation as defined in Section 12.1.2, noncompliance with the protocol conditions or AE).

### 3.7 Investigational Medicinal Product Preparation Storage and Accountability

### 3.7.1 Investigational Medicinal Product Storage and Security

The unblinded approved representative (e.g. pharmacist), will ensure that all IMP and any other study related material is stored in a secured area, under recommended temperature monitored storage conditions, in accordance with applicable regulatory requirements.

# 3.7.2 Investigational Medicinal Product Preparation

The unblinded approved representative (e.g. pharmacist), will ensure that all IMP and comparative treatment are reconstituted and dispensed by qualified staff members (Refer to 6.1 for details).

### 3.7.3 Investigational Medicinal Product Accountability and destruction

All IMP and any other study related material is to be accounted for on the IMP accountability log provided by the sponsor. It is essential that all used and unused supplies are retained for verification (by the sponsor or sponsor's representative). The pharmacist or nurse should ensure adequate records are maintained in the IMP accountability log.

All used and unused components of study preparation must be accounted for on the drug inventory log and will be returned to the sponsor at the completion or termination of the study, unless instructed otherwise by the sponsor.

# 3.8 Maintenance of Randomisation and Blinding

This study being investigator-blinded, the eCRF will provide two user profiles: one profile (e.g. pharmacist) which will be able to see the treatment arm and another one for the investigator for whom this information will be hidden. The tear-off of pack labels will indicate the treatment number to be entered in the eCRF, it will be similar for Eziclen®/Izinova® and Klean-Prep®. However, the appearance and contents of packs being different, to maintain the blinding for the investigator, the randomisation/dispensation of assigned treatment will be done by a pharmacist/nurse in charge of this activity. This person will be fully trained about the importance of his role in maintaining the blind for the investigator.

Two sets of individual sealed code break envelopes (refer to List B) will be prepared by the sponsor's randomisation manager to enable emergency code break procedures for individual subjects without compromising the blind of the study. One set will be provided to the investigational site and one set will be provided to the Global Patient Safety of the sponsor. The sending of code-break envelopes "investigator" will have to be coordinated with the sending of associated treatment kits.

Code break envelopes will only be opened in cases of medical emergency when treatment is dependent on knowledge of the IMP received.

**PAGE 34/103** 

In an emergency situation, which requires the identification of the study treatment group, the investigator may break the treatment code immediately, or as quickly as possible if he/she finds it is in the best interest of the trial subject.

Once it has been determined that knowledge of the treatment code is necessary, the investigator will ascertain the subject's identification number and treatment number and then break the blind for the subject concerned. The investigator will then sign date and provide reason for the code break on the Emergency Code break form and on the code break envelope.

At the earliest opportunity the investigator is requested to inform the monitor in charge of his/her centre that the blind has been broken for an emergency.

Monitors should routinely check the integrity of the envelopes that are stored at the study site. They must collect envelopes from the study site prior to study close out and ensure that they are all intact. If envelope(s) have been opened at the site or by the sponsor's representative, the monitor must ensure a written explanation is clearly documented (opener's name, dated signature and reason for opening) on the visit status page of the eCRF.

Confirmation of the integrity of all code break envelopes at study completion must be documented in the trial master file (TMF). All sets of the sealed individual subject envelopes must be kept in the TMF in the co-ordinating office at study completion for proof of integrity.

# 3.9 Source Data Recorded on the Case Report Form

Data will be collected in the eCRF in compliance with FDA 21 CFR Part 11. As required by GCP, the sponsor assigned monitor will verify, by direct reference to the source documents, that the data required by the protocol are accurately reported on the eCRF.

The source documents must, as a minimum, contain a statement that the subject is included in a clinical study, the date that informed consent was obtained prior to participation in the study, the identity of the study, diagnosis and eligibility criteria, visit dates (with subject status), IMP administration and any AEs and associated concomitant medication.

As required by ICH GCP Section 6.4.9, if some items are recorded directly on the eCRF and are considered as source data, the identification of these data must be documented and agreed between the investigator and the sponsor.

Definitions for source data and source documents are given below:

- **Source Data**: All original records and certified copies of original records of clinical findings, observations, or other activities necessary for the reconstruction and evaluation of the study. Source data are contained in source documents (original records or certified copies).
- **Source Documents**: Original documents, data and records (e.g. hospital records, clinical and office charts, laboratory notes, memoranda, subjects' diaries or evaluation checklists, pharmacy dispensing records, recorded data from automated instruments, copies or transcriptions certified after verification as being accurate copies, microfiches, photographic negatives, microfilm or magnetic media, x rays, subject files and records kept at the pharmacy, at the laboratories and at medicotechnical departments involved in the clinical study).

The subject must have consented to their medical records being viewed by the sponsor's authorised personnel, and by local and possibly foreign, Competent Authorities (CA). This information is included in the informed consent.

**PAGE 35/103** 

#### 4 SELECTION AND WITHDRAWAL OF SUBJECTS

#### 4.1 Inclusion Criteria

Subject MUST satisfy all of the following entry criteria before being allowed to participate in the study:

- (1) Provision of signed ICF to participate in the study obtained from the adolescent's parent(s)/ legal representative and a signed assent form from the adolescent according to local law
- (2) Male or female subjects between 12 to 17 years of age (inclusive)
- (3) Body weight more than 40 kg
- (4) Female of childbearing potential must have a negative pregnancy test
- (5) If female, and of child-bearing potential, subject must use an acceptable form of birth control (hormonal birth control, intrauterine device (IUD), double-barrier method, or depot contraceptive)
- (6) Routinely accepted indication for undergoing colonoscopy, including but not limited to polyposis coli diagnosis or surveillance, gastrointestinal bleeding, unexplained diarrhoea or constipation, surveillance of inflammatory bowel disease or confirmation of mucosal healing, abdominal pain, abnormal endosonography or manometry, anaemia of unknown aetiology, cancer surveillance
- (7) In the investigator's judgment, the parent(s)/legal representative are/is mentally competent to provide informed consent for the subject to participate in the study
- (8) In the investigator's judgement, subject is able and willing to follow study procedures including drug administration and response to questionnaires

### 4.2 Exclusion Criteria

If any of the following apply, the subject MUST NOT enter/continue in the study:

- (1) Subject with known or suspected ileus, gastrointestinal obstruction, gastric retention (gastroparesis), rectal impaction, toxic colitis, severe ulcerative colitis or toxic megacolon, advanced carcinoma, swallowing disorders
- (2) Subject with known or suspected inflammatory bowel disease (Crohn's disease, ulcerative colitis) in moderate to severe active phase defined by PCDAI >30 (Crohn's disease) or PUCAI >34 (ulcerative colitis)
- (3) Subject with bowel perforation or increased risk of bowel perforation, including connective tissue disorders or recent bowel surgery
- (4) Subject with previous significant gastrointestinal surgery (e.g. colostomy, colectomy, gastric bypass, stomach stapling)
- (5) Subject with uncontrolled pre-existing electrolyte abnormalities, or with electrolyte abnormalities based on Visit 1 laboratory results such as hypernatremia, hyponatremia, hyporahaemia, hypocalcaemia, uncorrected dehydration, or secondary to the use of medications such as diuretics or angiotensin converting enzyme (ACE) inhibitors judged clinically significant by the investigator
- (6) Subject with a prior history or current condition of severe renal (estimated glomerular filtration rate (eGFR) less than 30 mL/min/1.73 m2 as calculated by using the Schwartz bedside equation\* [13]), liver (ascites, Child-Pugh C), cardiac insufficiency (including congestive heart failure all grades) or hyperuricemia

**PAGE 36/103** 

- \*The estimated GFR will be calculated in patients with elevated creatinine at baseline.
- (7) Female subject who is pregnant or lactating
- (8) Subject who has participated in another investigational drug treatment within the last 90 days before the first study visit
- (9) Subject with phenylketonuria
- (10) Subject with history of asthma or hypersensitivity to any ingredient of either drug product
- (11) Subject for whom intake of substances likely to affect gastrointestinal motility or urinary flow rate is required
- (12) Subject with requirement to take any other oral medication within 3 hours of starting the bowel preparation, as this may impact medication absorption
- (13) Subject with tendency for nausea and/or vomiting
- (14) Subject with impaired consciousness that predisposes them to pulmonary aspiration or who have known swallowing disorders
- (15) Subject with history of major medical/psychiatric conditions that, in the judgment of the investigator, would compromise safety in the study
- (16) Subject with mental or psychiatric condition rendering the subject unable to understand the nature, scope and possible consequences of the study, and/or evidence of an uncooperative attitude
- (17) Subject with a condition that, in the opinion of the investigator, might increase the risk to the subject or decrease the chance of obtaining satisfactory data needed to achieve the objectives of the study
- (18) Subject who has previous enrolment in this study or concomitant enrolment in other clinical studies

# 4.3 Subject Withdrawal Criteria and Procedures

In accordance with the Declaration of Helsinki (in accordance with the applicable country's acceptance), each subject is free to withdraw from the study at any time. The investigator also has the right to withdraw a subject from the study in the event of concurrent illness, AEs, pregnancy (see Section 8.1.5), or other reasons concerning the health or wellbeing of the subject, or in the case of lack of cooperation. In addition, a subject may be withdrawn from the study as described in Sections 3.6, 5.2.4.2, 6.2 and 8.1.7.

Should a subject decide to withdraw from the study after administration of IMP, or should the investigator decide to withdraw the subject, all efforts will be made to complete and report the observations up to the time of withdrawal as thoroughly as possible. A complete final evaluation at the time of the subject's withdrawal should be made (see Section 5.2.4.2) and an explanation given of why the subject is withdrawing or being withdrawn from the study.

The reason for and date of withdrawal from the study must be recorded on the eCRF. If a subject withdraws consent, every attempt will be made to determine the reason. If the reason for withdrawal is an AE or a clinically significant laboratory test abnormality, monitoring will continue until the event has resolved or stabilised, until the subject is referred to the care of a local health care professional, or until a determination of a cause unrelated to the IMP or study procedure is made. The specific AE or test result(s) must be recorded on the eCRF. All evaluations should be performed, according to the protocol, on the last day the subject receives IMP, or as soon as possible thereafter. If the final visit is conducted more than 47 days after the

# IPSEN GROUP F-FR-58800-003 CONFIDENTIAL

# PROTOCOL: FINAL (INCLUDING AMENDMENT #6): 02 MARCH 2020

PAGE 37/103

dose of IMP, all safety evaluations will be performed. It is not planned to collect efficacy data after Visit 2.

**PAGE 38/103** 

# 5 STUDY PROCEDURES

# 5.1 Study Schedule

The schedule of procedures and assessments during the study is summarised in Table 4.

 Table 4
 Study Procedures and Assessments

Study Period	Baseline/	Colonoscopy	Phone	End of Study
	Treatment		contact	(or in case of Early Withdrawal*)
Visit	1	2	3	4
Day	Day 1	Day 2	Day 4	Day 32
Window	V		±1	-5/+15 i.e. Day 27 to Day 47
Eligibility Criteria	X			
Demographic Data	X			
Blood Pregnancy Test [a]	X			
Informed Consent (parent(s) or legal representative)	X			
Assent (subject)	X			
Medical and Surgical History	X			
Indication(s) for Colonoscopy	X			
Prior and Concomitant Medication [b]	X	X		X
Prior and Concomitant Non- Drug Therapy [b]	X	X		X
AEs [c]	X[d]	X	X[e]	X
Physical Examination	X X			X
Vital Signs (Temperature, blood pressure (BP) and heart rate (HR)	X	X		X
Body Weight and height[f]	X	X		X
Blood sample collection [g], [h]	X[i]	X[j]		X
Urine sample collection[k]	X	X		X
Blood and urine sulphates[1]	X	X[j]		X
RANDOMISATION [m]	X	- U		
Study treatment dispensation (with explanation of treatment administration)	X X			
Subject/caregiver leaflet dispensation by study nurse (with explanation of questionnaires including compliance measurement)	X			
Subject takes treatment preparation	X			
Completion of leaflet questionnaires by subject/ caregiver/ nurse				
• Treatment / Compliance	X			
Treatment     Acceptability	X			

**PAGE 39/103** 

Study Period	Baseline/ Treatment	Colonoscopy	Phone contact	End of Study (or in case of Early Withdrawal*)
• Symptom Scale (Tolerability)	X			
Collection of leaflet questionnaires by study nurse		X		
Drug accountability/ study administration compliance by unblinded site member		X		
Colonoscopy assessment [n]		X		
Subject status at the end of the visit	X	X	X	X

\*Early withdrawal will be anytime from Visit 1 (Refer to Section 3.6)

- [a] If applicable. Urine pregnancy test will be performed only when blood tests including pregnancy have been performed prior to Visit 1.
- [b] Prior and concomitant medication and non-drug therapy will from 7 days before baseline and for any action taken by the investigator
- [c] AEs will be actively collected by the investigator and subjects will be instructed to contact the investigator if they experience any AEs
- [d] At baseline, AEs will be collected from the date of informed consent and assent signature
- [e] The investigator will contact the subject by phone on Day 4±1 to collect data on potential AEs
- [f] Height will be measured at Baseline only
- [g] Local laboratory (blood): biochemistry including: anion gap, alanine aminotransferase (ALT), aspartate aminotransferase (AST), creatine phosphokinase (CPK), lactic dehydrogenase (LDH), gamma-glutamyl transferase (GGT), total and conjugated bilirubin, creatinine, urea, serum electrolytes (sodium, potassium, chloride, calcium, magnesium, phosphorus, bicarbonate), alkaline phosphatase, albumin, total protein, C reactive protein (CRP), uric acid, creatinine clearance (calculated GFR), osmolality
- [h] Laboratory assessments performed within 10 days or less prior to inclusion may be used to determine eligibility upon investigator agreement.
- [i] Additional local laboratory haematology: complete blood count (CBC), international normalised ratio (INR), (Section 8.2.1)
- [j] Blood sampling during anaesthesia
- [k] Local laboratory urine analysis (by dipstick), microscopic examination
- [1] Collection of blood and urine sample for central laboratory sulphate dosage
- [m] Randomisation if satisfactory biochemistry results
- [n] Colonoscopy assessment: Rescue treatment, cleansing Score, BBPS, start time of colonoscopy, time of caecal intubation, caecum reached, withdrawal time, diagnosis/findings.

Table 5 Subject's Leaflet Collected Information

	During/after Dose 1 Day 1	During/after Dose 2 Day 1
Treatment/Compliance Questionnaire[a]	X	X
Treatment Acceptability Questionnaire	X	X
Symptom Scale (Tolerability)	X	X
Information about time to bowel movement		X
and time to first clear watery stool.		

a Treatment/Compliance questionnaire will collect information about: preparation of treatment, treatment intakes (recording of residual volumes, start/end times) for Eziclen®/Izinova® or Klean-Prep®.

The total volume of blood drawn for all evaluations throughout this study is approximately 16.5 mL for each subject.

The total amount of blood to be collected from all subjects is presented in Table 6.

Table 6 Blood Volume Calculation

Description	Number of Samples	Volume (mL)	Total Volume (mL)
Haematology	1	3 mL	3 mL
Biochemistry	3	2.5 mL	7.5 mL
Sulphates	3	2 mL	6 mL
Total Volume (mL)			16.5 mL

# 5.2 Study Visits

# 5.2.1 Prescreening Period

The prescreening period is defined as the period between the visit where the colonoscopy indication is posed and the date of Visit 1. During this period, and prior to the study entry, the investigator, or a person designated by the investigator, will explain the nature, purpose, benefits and risks of participation in the study to each subject and subject's parent (s) or legal representative. An ICF will be provided to each parent/legal representative, and an assent form will be provided to each subject during the pre-screening period, when the indication for colonoscopy is decided. The documents are to be dated and signed before any study screening procedures, according to local IRB/IEC requirements.

# 5.2.2 Baseline/Treatment visit (Visit 1)

Each subject's assent and subject's parent(s)/legal representative consent forms, signed and dated will be retained by the investigator. The subject will be hospitalised and will be allocated a subject number. All subjects must be identifiable throughout the study. The investigator will maintain a list of subject numbers and names to enable records to be found at a later date if required. The baseline visit (Visit 1) will take place on the day of hospitalisation for bowel preparation administration, after retrieving the signed ICF and assent form.

Dietary recommendations for this study are as follows: subjects will come on the morning of Visit 1 under fasting conditions. Starting with breakfast, the subjects may only have clear liquids on the day prior to colonoscopy until completion of the colonoscopy the following day. Non-adherence to the dietary recommendations (nature and date/time) will be recorded in the patient leaflet.

The following baseline assessments will be performed by the investigator/study nurse:

- Eligibility check (inclusion/exclusion criteria)
- Demographic data (date of birth/age, sex),
- Medical and surgical history, including ongoing medical history, as well as any significant conditions, including but not limited to major abdominal surgeries (excludes appendectomy), renal failure/dysfunction, liver failure/dysfunction, cardiac disorders inflammatory bowel disease, polyposis, diabetes, cancer (must indicate type of cancer), immune system disorders, electrolyte abnormalities
- Physical examination

1 depending on regulatory requirements, the date of birth may not be collected entirely, only the year will be collected

-

PAGE 41/103

- Pubertal stage, if available (Tanner stage)
- Body weight and height
- Vital signs (temperature, supine and standing BP and HR)
- Blood sampling: Laboratory assessments performed within 10 days or less prior to inclusion may be used to determine eligibility upon investigator agreement.
  - a) haematology: international normalised ratio (INR), CBC
  - b) biochemistry including: anion gap, ALT, AST, CPK, LDH, GGT, total and conjugated bilirubin, albumin, creatinine, urea, serum electrolytes (sodium, potassium, chloride, calcium, magnesium, phosphorus, bicarbonate), alkaline phosphatase, total protein, CRP, uric acid, creatinine clearance (calculated GFR), osmolality
- Urine analysis by dipstick (pH, protein, ketones, bilirubin, blood, urobilinogen, nitrites, leukocytes, glucose and specific gravity, urine microscopic examination
- Blood and urinary samples for sulphate measurement
- Blood pregnancy test, if female of child-bearing potential. Urine pregnancy test will be performed only when blood tests including pregnancy have been performed prior to Visit 1.
- Indication(s) for colonoscopy to be collected
- Randomisation
- Drug accountability, study treatment dispensation by study nurse (with explanation of treatment administration)
- Subject/caregiver questionnaires dispensation by study nurse (with explanation of questionnaires including compliance measurement)
- Prior and concomitant medications including supplements, herbal medications and nonprescribed compounds
- Prior and concomitant non-drug therapies and surgical procedures
- Collection of AEs from the time of informed consent signature
- Subject status at the end of the visit

Records up to the time of premature termination should be completed. In the event that the subject was not receiving IMP, the primary reason will be recorded.

If any Visit 1 serum chemistry result is considered abnormal and clinically significant by the investigator result may be checked per investigator's decision. The abnormal significant result will be reported as an AE.

In case of non-inclusion of the subject, the primary reason will be recorded.

Following confirmation of eligibility for the study, subjects will be given a randomisation/treatment allocation number and allocated to one of the dosing groups specified in Section 6.1.

Caregivers and subjects will be provided with a subject leaflet containing instructions on how to administer the study preparation. Caregivers will be provided with a Treatment Acceptability Questionnaire (see Section 7.3.2.3) to report their child's experience with the study preparation, and a Symptom Scale to rate subject tolerability (see Section 8.6). Subjects/caregivers will complete these questionnaires during and after the treatment administration.

Subjects will be hospitalised for preparation. The treatment will be prepared by a nurse and administration will be monitored as described in Section 3.4. The nurse or caregiver will fill in

PAGE 42/103

the questionnaires or ensure that the subject fills in, as appropriate. If a subject is unable to complete the preparation, a nasogastric tube will be placed.

The bowel cleansing preparation will be taken orally on the evening of the day before colonoscopy.

The following procedures will be performed during and after treatment administration:

- Treatment preparation taken by subject (nasogastric tube may be placed if needed for completion of preparation)
- Completion of subject leaflet (for Eziclen®/Izinova® or Klean-Prep® depending on allocated treatment arm) which contains:
  - o Treatment administration, compliance, Treatment Acceptability Questionnaires and Symptom Scale by subject/caregiver
  - o Information about bowel movement and stool
  - o Time of first clear watery stool

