# 3.5 Study Duration

This study will consist of a 1-day enrolment (Day 1, baseline) and investigator-blind label dosing period, a 1-day colonoscopy (Day 2) and a 30-day follow-up period (Day 32 (-5/+15, i.e. Day 27 to Day 47). Subjects are expected to participate in this study for a minimum of 27 days and up to 47 days.

The subject's participation in the study will be considered to have ended at the time of the last visit (30 days after last IMP intake).

The study will be considered to have started when the first subject has been screened and provided signed informed consent. The Baseline visit (Visit 1) will be performed on the same day of treatment administration. Subjects meeting all eligibility criteria will be randomised to receive either Eziclen®/Izinova® or Klean-Prep® solution. After having received either Eziclen®/Izinova® or Klean-Prep® solution, subjects will undergo colonoscopy. Subjects will be contacted by phone on Day 4 and will come on Day 32 for a safety follow-up visit.

As the blood and urine sulfate assay are not standard tests, the samples are transported in batches to an overseas central laboratory and processed there. Results are transferred to the study database. The last sample is taken at the time of last subject last visit. The estimated duration for transfer of the sample to the central laboratory, processing and transfer of the results to the database is approximately 6 weeks. In order to ensure that the sulfate data are included in the CSR, the end of study is being redefined. The study will be considered to have ended after the last subject last external data from central laboratory has been transferred to the database.

The overall duration of the study will be approximately 32 months (30 months of recruitment + 1 month of follow-up + 6 weeks minimum for last data transfer).

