3.2.2.1 Adverse events

All AEs will be coded according to MedDRA (last version used for coding during the study course) and will be classified by MedDRA preferred term (PT) and system organ class (SOC). AE listings will be presented by subject, SOC and PT for all AEs, serious AEs (SAEs) and AEs leading to withdrawal on the safety population.

A TEAE is defined as any AE that occurs during the active phase of the study if:

it was not present prior to receiving the first dose of IMP

or

• it was present prior to receiving the first dose of IMP but the intensity increased during the active phase of the study.

All TEAEs will be flagged in the AEs listings.

An overall summary table of all AEs will be presented with the number of AEs and the numbers and percentage of subjects with exact 95 % CI for each of the following categories:

- Any AEs,
- Any SAEs,
- Causality of SAEs,
- Any TEAEs,
- Intensity of TEAEs,
- Causality of TEAEs,
- Causality and intensity of TEAEs,
- Any TEAEs leading to death,
- Any TEAEs leading to withdrawal.

In the event of multiple AEs being reported by the same subject, each subject is counted for each intensity level, each causality level or each intensity and causality combined level. That means that the total number of subjects for all levels of intensity/causality might be higher

than the overall number of subjects with at least one AE. Related adverse events are those events with causality missing or related.

Incidence by SOC/PT of all reported TEAEs, related TEAEs, SAEs and TEAEs leading to withdrawal of study medication will be tabulated by treatment group and overall. In addition, summary tables by SOC/PT will present TEAEs by maximum intensity and drug relationship and will present TEAEs with incidence ≥ 2 %. And a summary table will present TEAEs by decreasing frequency of PT.

In the event of multiple occurrence of the same AE (same PT) being reported by the same subject, the maximum intensity (severe > missing > moderate > mild) and the most serious causality (related > not related) for each concerned PT will be chosen.

Moreover, the summary table will be duplicated by sex, age class and weight class, as well as the summary table of the incidence of TEAEs by SOC and PT.

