3.2.4 Subject disposition

A listing of the randomisation numbers will be presented by treatment group and subject.

The number and percentage of subjects screened and included in each population will be presented by treatment group for the screened population and by country and centre. In addition, a flow chart will be provided with the number of subjects in each analysis population as well as colonoscopy performed and completed.

A listing of the inclusion and exclusion criteria will be provided by treatment group and subject, and subject eligibility will also be listed.

The reasons for subject exclusions from each population will also be tabulated by treatment group and overall on the randomised population.

A summary table will present the extent of subject exposure in the study for each treatment group by deriving the study duration defined as the number of days from the date of consent to the last study visit.

Listings of dates of assessments (relative day), of hospitalization entry and discharge and of study duration will be presented by treatment group and subject. The number and percentage of subjects at each planned visit during the study will be presented by treatment group and overall for the Safety population.

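### SAEs are collected from consent and tabulated by arm, and the SAP text mentions no treatment-emergent SAE summary, so an SAE from before first intake can enter an arm's incidence

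*Protocol*

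**What the plan says.** **Start of collection.** Protocol 5.2.2 lists "Collection of AEs from the time of informed consent signature" among the Visit 1 tasks. Footnote [d] to Table 4 agrees: "At baseline, AEs will be collected from the date of informed consent and assent signature". Protocol 8.1 and SAP 1.4.2.2 use the same starting point, and the AE definition in Protocol 8.1.1 covers time when no study product has been given.

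**Timing of consent.** Under Protocol 5.2.1 the forms are provided "during the pre-screening period, when the indication for colonoscopy is decided" and must be signed before any screening procedure. Under 5.2.2, Visit 1 takes place "after retrieving the signed ICF and assent form". No maximum interval is stated. The schedules (Protocol Table 4, SAP Table 5) mark consent and assent under Visit 1. The first intake is on the evening of Day 1 (Protocol 6.1).

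**Tabulation.** SAP 3.2.2.1 plans "Incidence by SOC/PT of all reported TEAEs, related TEAEs, SAEs and TEAEs leading to withdrawal of study medication", by treatment group and overall. Protocol 10.4.7 likewise has TEAEs and SAEs tabulated by group. On causality the SAP says: "Related adverse events are those events with causality missing or related".

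**Duration.** SAP 3.2.4 presents the extent of exposure by "deriving the study duration defined as the number of days from the date of consent to the last study visit". Protocol 3.5 says: "Subjects are expected to participate in this study for a minimum of 27 days and up to 47 days".

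**The concern.** Comparing safety between the two preparations is a stated secondary objective. An event with onset before the first portion is drunk cannot be an effect of either preparation. If it is counted in the SAE incidence of the arm the subject later joins, the table mixes background illness during the wait for colonoscopy with events after dosing. The same table treats deaths and withdrawals as treatment-emergent, so its rows do not share one time origin. When SAEs are few, even a single event from before dosing is visible in such a table. The duration table raises a smaller, related point: a figure that starts at consent is presented as exposure.

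**Working it through.** This is mainly a check of text, with some illustrative arithmetic.

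**1. Can an SAE before first intake be collected?** Yes, if consent is signed before Day 1. Collection starts at signature (Protocol 5.2.2, 8.1; SAP 1.4.2.2), and nothing limits the time from signature to Visit 1 (Protocol 5.2.1, 5.2.2).

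**2. Does the analysis set remove it?** No. The safety population (SAP 2.2) selects randomised subjects with at least a partial dose. It filters subjects, not event onset.

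**3. Does the table plan remove it?** The items in SAP 3.2.2.1 compare as follows.

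| Item | All events | Treatment-emergent |
|---|---|---|
| Summary: any event | yes | yes |
| Summary: intensity, causality | no | yes |
| Summary: death, withdrawal | no | yes |
| Summary: any serious event | yes | not mentioned |
| Summary: causality of serious events | yes | not mentioned |
| SOC/PT: all, related, leading to withdrawal | no | yes |
| SOC/PT: serious events | yes | not mentioned |

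Only the serious-event items lack a treatment-emergent version. The sentence introducing the summary table does not itself say that it is by arm, but Protocol 10.4.7 does so for SAE incidence.

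**4. Direction of the effect.** Consent precedes randomisation, and randomisation and first intake fall on the same day. Events before dosing are therefore essentially independent of allocation and add, on average, the same small incidence c to both arms. For low incidences pA and pB, the difference (pA + c) − (pB + c) = pA − pB is unchanged in expectation, while the ratio (pA + c)/(pB + c) moves towards 1. Variability increases. There is no systematic tilt towards one arm.

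**5. Size.** Neither document gives the wait w from consent to first intake, or an SAE rate. Both are assumptions here.

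- The time from dose to last visit, f, is 32 − 1 = 31 days, with a window of 27 − 1 = 26 to 47 − 1 = 46 days (Protocol 3.5).
- The share of collection time before first intake is w/(w + f):
  - w = 0: 0%
  - w = 1: 1/32 = 3% (2 to 4% across the window)
  - w = 10: 10/41 = 24% (18 to 28%)
  - w = 30: 30/61 = 49% (40 to 54%)
- These are shares of time, not of SAEs. They would equal shares of SAEs only if the daily rate were the same before and after dosing.
- Suppose the background rate were 0.5% to 2% per subject per 30 days, with the planned 125 per arm. Expected SAEs before dosing per arm would be 125 × rate × w/30. That is 0.2 to 0.8 at w = 10, 0.6 to 2.5 at w = 30, and 0 at w = 0.

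**6. Study duration.** SAP Appendix 1 item (2) defines it as last visit minus consent date, plus 1. With consent on Day 1 this gives (27 − 1) + 1 = 27 and (47 − 1) + 1 = 47 days, which reproduces the protocol's range. With consent w days earlier the maximum becomes 47 + w, for example 57 days at w = 10. The quantity matches the protocol's range only when w = 0.

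**The case against.** The case on the other side is substantial, and much of it stands.

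- **The wait may be zero.** The schedules place consent at Visit 1, and Protocol 5.2.1 says when forms are handed out, not that they are signed early. This stands as a limit on size. Retrieving forms already signed still allows an earlier signature, and no interval is set.
- **A reader might infer that the comparison is biased against one preparation.** The documents do not support that: events before randomisation balance in expectation.
- **A reader might take the time shares above as shares of SAEs.** That needs equal daily rates. The period after dosing contains the preparation, anaesthesia and colonoscopy. A subject with an SAE while waiting must still pass eligibility, including exclusions 5, 15 and 17. Preplanned admissions are not SAEs (Protocol 8.1.4). All of these point to a smaller share of SAEs.
- **A reader might expect falsely related SAEs from the missing-causality rule.** This is unlikely. Investigators must record causality (Protocol 8.1.3), the sponsor asks for it when an SAE report lacks it (8.1.4), and an implausible time sequence is a ground for classifying an event as not related (8.1.2.2).
- **A reader might conclude that no serious-TEAE table is planned at all.** Only the SAP text can be checked. The list of tables in Appendix 3 is blacked out, and the templates are in a separate document.
- **Listings already flag TEAEs.** True, and a careful reader could separate the events by hand. A flag in a listing does not give the by-arm incidence that the safety objective calls for.

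**Conclusion.** The point holds in a limited form. As the SAP text stands, an SAE with onset between consent and first intake, in a subject later dosed, counts in that arm's SAE incidence, and the text offers no treatment-emergent SAE summary to set beside it. The effect is noise and some pull of relative comparisons towards 1, not systematic bias. Its size cannot be derived from the documents. It is about zero if consent is signed on Day 1 and grows with a wait that the protocol does not limit. The conclusion assumes that at least some subjects sign before Day 1 and that the blacked-out table list does not already contain the missing tables. Collecting AEs from consent is ordinary practice and is not at fault, so Protocol 5.2.2 needs no change. The duration point is minor and is one of labelling: SAP 3.2.4 states openly how the figure is defined, and the volumes taken are summarised separately in SAP 3.2.1.2.10.

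**What to change.** In SAP 3.2.2.1:

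- Keep the all-SAE rows and the all-SAE SOC/PT table. Removing them would conflict with Protocol 10.4.7.
- Add rows for any serious TEAEs and for causality of serious TEAEs, and a serious-TEAE SOC/PT table, all by arm. Name these as the basis for the safety comparison.
- Show SAEs with onset before first intake on one separate line.
- Apply the rule that missing causality counts as related to TEAEs only.

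In SAP 3.2.4 and Appendix 1 item (2), report follow-up from first intake to last visit beside the consent-based study duration, and do not label the latter as exposure.

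The cost is a few lines of SAP text and a filter on the TEAE flag that already exists. No new data are needed. Events with missing or partial onset dates are assumed treatment-emergent unless other data indicate otherwise (SAP 3.2.3.2), so the filter does not drop an event merely because its date is incomplete.
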